14.1.3 Supplementary Analyses of the Primary Efficacy Endpoint EFS

The following supplementary analyses will be performed.

Table 7: Supplementary analysis for EFS

Supplementary analysis	Population	Censoring rules (Table 4)	Endpoint	Statistical methods
1	ITT	Sensitivity #1	EFS as assessed by the BIRC	same as primary EFS analysis (Section 14.1.1), incl. Kaplan-Meier curves
2	ITT	Sensitivity #2	EFS as assessed by the BIRC	same as primary EFS analysis (Section 14.1.1), incl. Kaplan-Meier curves

Multivariable Cox Regression

Multivariable Cox regression analysis will be conducted for the primary endpoint EFS as assessed by the BIRC to assess and adjust the treatment effect for relevant baseline factors of potential prognostic impact. The subgroup variables defined in Sections 8.2.1 and 8.2.2 will be included in the model. A stepwise selection procedure will serve to identify explanatory variables of potential prognostic values additional to the randomization strata, which will be included in all models during the selection procedure. The stepwise selection method in SAS (PROC PHREG) will be used. The level of significance for an explanatory variable to enter the model is set to 0.15 (boundary for p-value of Score test for inclusion) and the significance level for removing it is set to 0.40 (boundary for p-value of Wald test for exclusion). Once the selection procedure is finalized, the treatment group will be added to the effect of treatment on EFS when adjusted for the selected explanatory variables.

The Cox's Proportional Hazard model is defined as: $h(t) = h(0;t) \exp(Xb)$, where h(0;t) defines the Baseline Hazard function, X defines the vector of explanatory variables and b the unknown vector of regression parameters. The HR of all selected explanatory variables and of treatment effects will be reported including 2-sided 95% CIs. No interaction will be considered. Post-Baseline factors will not be considered for the model.

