8.2.1 Randomization stratification factors (from IWRS)

The following subgroups are relevant for all endpoints listed in Section 8.2.

Region

- North America
- Western Europe (as defined in Appendix 4) (reference level)
- Rest of the World

Primary tumor site

- Larynx
- Other (Oropharynx and Hypopharynx) (reference level)

Lymph node involvement

- N0-1 (reference level)
- N2
- N3

T size

- T4
- Other (T1, T2, T3) (reference level)

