8.2.2 Other subgroups

The following subgroups are only relevant for the primary efficacy endpoint EFS (BIRC assessed) and the secondary efficacy endpoint OS.

Age Group 1

- Age < 65 years (reference level)
- Age \geq 65 years

Age Group 2

- Age < 70 years (reference level)
- Age \geq 70 years

Sex

- Male (reference level)
- Female

Race

- Asian
- American Indian or Alaska Native
- Black or African American
- Native Hawaiian or Other Pacific Islander
- White (reference level)
- Other

Ethnicity

- Hispanic or Latino
- Not Hispanic or Latino (reference level)

Note: Race or Ethnicity category "not reported" will be handled as "missing"

Primary tumor site (as recorded in the eCRF):

- Larynx (reference level)
- Hypopharynx
- Oropharynx

Eastern Cooperative Oncology Group Performance Status (ECOG-PS)

- 0 (reference level)
- ≥1

American Joint Committee on Cancer (AJCC) cancer staging

- III (reference level)
- IVA
- IVB

Alcohol

- current use
- no current use (reference level)

Smoking

- current use (reference level)
- history of use
- no history of use

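### The stepwise Cox model for EFS selects covariates on complete cases and can hold tumour site in two overlapping codings (minor; supplementary analysis only)

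*SAP*

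**What the plan says.** SAP 14.1.3 plans a multivariable Cox model for BIRC-assessed EFS that adjusts the treatment effect for baseline factors. On the candidates it says "The subgroup variables defined in Sections 8.2.1 and 8.2.2 will be included in the model". On the method it says "The stepwise selection method in SAS (PROC PHREG) will be used". A variable enters by score test: "The level of significance for an explanatory variable to enter the model is set to 0.15", with removal at 0.40. The search is for variables "additional to the randomization strata, which will be included in all models during the selection procedure". Treatment is added once selection is finished, and "The HR of all selected explanatory variables and of treatment effects will be reported including 2-sided 95% CIs".

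Three other parts of the SAP bear on this list.

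- **Missing values.** Race and ethnicity are both in SAP 8.2.2, which adds: "Note: Race or Ethnicity category 'not reported' will be handled as 'missing". SAP 8.2 leaves the missing category out of subgroup analyses. SAP 9.12 imputes nothing unless stated otherwise. SAP 14.1.3 gives no rule for missing covariates in this model.
- **Analysis set.** The opening of SAP Section 14 makes ITT the default for efficacy analyses.
- **Tumour site.** SAP 8.2.1, headed as coming from the IWRS, has larynx against "Other (Oropharynx and Hypopharynx) (reference level". SAP 8.2.2 lists "Primary tumor site (as recorded in the eCRF") again, now with larynx, hypopharynx and oropharynx as separate levels and larynx as reference. SAP 8.2 says that subgroup levels come from the eCRF, which does not fit the 8.2.1 heading.

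**The concern.** A supplementary adjusted HR is useful if it describes the same participants as the main result. Here the covariate search would use only participants with every candidate recorded, and whether race or ethnicity was reported has nothing to do with the EFS question. The text does not say whether the final fit returns to all randomized participants. If it does not, or if race or ethnicity is retained, the adjusted HR departs from the ITT default without saying so.

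The site variable raises a separate question. The plan commits to printing HRs for the selected covariates. Two codings of the same anatomical fact in one model can leave one of those HRs undefined, or make it depend on a few records where the IWRS and the eCRF disagree.

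**Working it through.** **Base figures.** The plan gives 700 participants (protocol 10.2.1), 429 EFS events (SAP Tables 2 and 3), an assumed HR of 0.73 (note to Table 3) and 1:1 allocation. It gives no figure for the multivariable model. The design figures behind it do reproduce. Three looks at 279, 365 and 429 events with O'Brien-Fleming-type spending give HR boundaries of 0.737, 0.793 and 0.821. Power is 88.2% when the first-look futility bound is followed, as in Table 3.

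**Missing covariates.** Let x be the share with race or ethnicity not reported. The documents do not give x, so it is assumed, with equal event rates in those dropped. PROC PHREG was not run; deletion of records with a missing listed covariate is taken as its default.

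- Events kept = 429(1 − x)
- SE of the log HR = 2/√events; with all events, 2/√429 = 0.0966
- Increase in SE = 1/√(1 − x) − 1
- 95% CI at HR 0.73 = exp(ln 0.73 ± 1.96 × SE); with all events, 0.604 to 0.882

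| x | Participants lost | Events kept (lost) | SE | Increase | 95% CI at 0.73 |
|---|---|---|---|---|---|
| 2% | 14 | 420 (9) | 0.0975 | 1.0% | 0.603–0.884 |
| 5% | 35 | 408 (21) | 0.0991 | 2.6% | 0.601–0.886 |
| 10% | 70 | 386 (43) | 0.1018 | 5.4% | 0.598–0.891 |
| 20% | 140 | 343 (86) | 0.1080 | 11.8% | 0.591–0.902 |

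These losses always apply to the selection step. They apply to the final treatment HR only if the selection data set is carried forward, or to the extent that race or ethnicity is selected.

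**Site coded twice.** Take four columns: a constant (the role of the baseline hazard), IWRS larynx, eCRF hypopharynx and eCRF oropharynx. If the two sources agree for everyone, IWRS larynx = 1 − hypopharynx − oropharynx. The rank is then 3 for 4 columns, and one site contrast has no unique estimate. If the eCRF rule in SAP 8.2 governs both codings, this dependence is exact by construction.

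If a share d of participants is discordant regardless of site, the IWRS indicator varies within eCRF site with variance d(1 − d). The SE of its log HR is then about 1/√(429 × d(1 − d)).

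- Without the eCRF variable, assuming 25% larynx: 1/√(429 × 0.25 × 0.75) = 0.11
- With it, at d = 0.5%, 1%, 2% and 5%: 0.68, 0.49, 0.34 and 0.22. A simulated design gave 0.69, 0.48, 0.35 and 0.22.

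At d = 1% the contrast rests on about 7 of 700 participants.

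**Effect on treatment.** In a simulation with full agreement and equal hazards for hypopharynx and oropharynx, the treatment HR was 0.736 with and without the second site coding (SE 0.0927 and 0.0925). The three-level variable entered with probability 0.15, the nominal level.

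**Age cuts.** The 65- and 70-year indicators have full rank. Variance inflation is about 1.5 to 1.7 under assumed age distributions (means 60 to 64, SD 8 to 9). Together they define three age bands.

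**The case against.** The best defence is that every consequence is conditional. Selection and the final fit are separate steps, and nothing in SAP 14.1.3 says that the final fit keeps the reduced data set. If race and ethnicity are not selected and the model is refitted, no participant is lost on their account. If few values are unreported, the loss is trivial. The second site coding matters only if it enters, and then it disturbs a covariate HR and not the treatment HR. The ITT label on this model comes only from the general default in Section 14; Table 7 attaches it to the two censoring-rule analyses.

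All of that stands, and it limits the point. It does not remove it. Run as written, and given the default deletion, selection uses complete cases as soon as one value is missing. The data set for the final fit is left open, and nothing prevents both site codings from being in one model.

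A reader might also infer that the two age cuts are collinear, or that AJCC stage must go because T and N are forced in. Neither follows. The age cuts are estimable together. The forced T factor is only T4 against other, while SAP 11.3 records T4a and T4b, so the documents do not show stage to be redundant.

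**Conclusion.** The point holds as a minor, cost-free improvement to a supplementary analysis. Covariate selection runs on complete cases. The adjusted treatment HR loses participants only under the two conditions given. If it does, the cost is about 9 to 86 of 429 events and a 1.0% to 11.8% larger SE, for an assumed not-reported share of 2% to 20%. One site contrast can become inestimable or rest on a handful of discordant records, if the three-level variable is selected.

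It would be tempting to say that the adjusted HR is certain to leave out participants, or that site HRs cannot be interpreted. The documents do not support either statement: the not-reported rate and the final data set are unstated, and without the second coding the larynx-against-other HR is an ordinary estimate. The stratified log-rank test, the main Cox HR, the stratified Cox HR (SAP 14.1.1) and the power figures use none of the 8.2.2 variables and are unaffected. No alpha is attached to this model.

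The conclusion rests on PROC PHREG's default deletion, equal event rates in those dropped, and the assumed shares and site mix.

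**What to change.** Add a few sentences to SAP 14.1.3 before unblinding:

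- For this model, keep not reported as its own level for race and ethnicity, or remove both from the candidates. A separate missing category is already the SAP's practice for qualitative summaries (Section 9).
- Fit the final model on all ITT participants with the selected covariates, and print the participants and events used at selection and in the final fit.
- Use one tumour-site coding from one source. Either keep the forced IWRS factor and drop the eCRF variable from the candidates, or use the three-level eCRF variable in its place and say so.
- Reconcile the eCRF rule in SAP 8.2 with the IWRS heading of 8.2.1.

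Offering a single age variable is optional tidying. AJCC stage can stay. The cost is SAP wording and minor programming, with no new data.

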14.1.4 Subgroup Analyses of the Primary Efficacy Endpoint EFS

Subgroup analyses for the EFS as assessed by the BIRC and EFS as assessed by investigator (with primary censoring rule as defined in Table 4) will be performed by treatment arm for all subgroup levels defined in Sections 8.2.1 and 8.2.2. In the case of a low number of participants within a category (<5% of the randomized population), the categories may be pooled. All subgroup analyses are exploratory and will be performed unstratified. No adjustment for multiplicity will be performed.

Cox regression models will be fitted for the EFS time as dependent variable and with subgroup type, the treatment arm, and with and without the treatment by subgroup type interaction as explanatory variables. The unstratified HR and its corresponding 95% CI will be computed per subgroup level. A p-value for the interaction test (Likelihood Ratio test) comparing models with

and without the interaction term will be provided together with the hazard ratios and corresponding 95% CI of the interaction model parameter.

The HR and its corresponding 95% CI, overall and for each subgroup level will be presented in a forest plot.

14.2 Secondary Efficacy Endpoints and Analyses

This section describes the statistical methods for the analysis of the secondary efficacy endpoints. All secondary endpoint analysis will be performed on ITT. Confirmatory testing will only be done for OS. For all other secondary endpoints, no formal statistical hypotheses will be tested.

14.2.1 Overall Survival

Overall Survival (OS) time is defined as the time (in months) from randomization to death due to any cause.

$$OS = (date \ of \ death - randomization \ date +1) / 30.4375$$

Participants without documented death at the time of analysis will be censored at the date of last known contact.

The treatment difference in OS between the 2 treatment arms will be assessed using a one-sided stratified log-rank test as described for the primary analysis of EFS in Section 14.1.1. The significance boundaries are adjusted accordingly to control the family-wise error rate (FWER) at 2.5% one-sided (see also Table 3). The stratification factors are tumor size (T4 vs other) and lymph node involvement (N0-1 vs N2 vs N3).

The null and alternative hypotheses can be described in terms of hazard ratios as:

$$H_0^{OS}$$
: $\lambda_{(xevinapant + CRT)} / \lambda_{(placebo + CRT)} \ge 1$ versus

$$H_1^{OS}$$
: $\lambda_{(xevinapant + CRT)} / \lambda_{(placebo + CRT)} < 1$,

where $\lambda_{(xevinapant + CRT)}$, $\lambda_{(placebo + CRT)}$ represents the hazard of OS for the (xevinapant + CRT) and the (placebo + CRT) group respectively.

The treatment effect will be analyzed using a Cox Proportional Hazard model as described for the primary analysis of EFS in Section 14.1.1 including the RCI for the hazard ratio.

A further sensitivity analysis to address possible biases due to the dynamic allocation process will be performed based on permutation testing for the secondary endpoint OS as described for the primary endpoint EFS by BIRC in Section 14.1.2.

The Kaplan-Meier method (as described for the primary analysis of EFS in Section 14.1.1) will be used to estimate the OS in each treatment arm. Survival rates at 12, 24, 36, 48, and 60 months after randomization will be estimated with corresponding two-sided 95% CIs.

Graphical representation of the survival curves (Kaplan-Meier estimates) as step functions will be provided per treatment arm and per stratification variable.

The number and percentage of deaths will be presented by treatment arm. The OS time or censoring time will also be listed.

The same subgroup analyses as described for the EFS in Section 14.1.4 will be performed for OS.

Table 8: Estimand Attributes OS

Objective	Estimand Attributes
Secondary	
To demonstrate improvement in	Endpoint: OS defined as the time from date of randomization to death
Overall Survival (OS) with xevinapant compared to placebo when added to chemoradiotherapy	Population: Patients with LA-SCCHN Stage III, IVA or IVB suitable for definitive CRT
	Treatment: Xevinapant and CRT followed by xevinapant followed by subsequent cancer therapy vs. placebo and CRT followed by placebo followed by subsequent cancer therapy
	Intercurrent Event Strategy: The endpoint will be analyzed regardless of whether or not the following intercurrent events had occurred (treatment-policy strategy):
	Treatment discontinuationStart of subsequent anticancer therapy
	Population-level Summary: Hazard ratio

Follow-up for OS

In order to assess the follow-up for OS, Kaplan-Meier estimates will be calculated using the censoring rules with reverse censoring indicator.

14.2.2 Progression-Free Survival

Progression-Free Survival (PFS) time according to RECIST v1.1 is defined as the time (in months) from randomization to the first occurrence of disease progression (radiological or clinical, as assessed by the BIRC or the investigator, respectively) or death due to any cause.

PFS =
$$(date \ of \ PD \ or \ death - randomization \ date +1) / 30.4375$$

Censoring rules for the primary and sensitivity analyses of PFS are described in Table 9 below. The last adequate tumor assessment is defined as the last tumor assessment result that is not "Not evaluable" or "Not assessed". If a participant is meeting a multiple censoring situation, the earliest censoring criterion will be applied.

Table 9: Censoring rules for PFS

Situation	Primary	Sensitivity #1	Sensitivity #2
No evaluable baseline or post-baseline assessment*	Right censored at the date of randomization	Right censored at the date of randomization	Right censored at the date of randomization
Death, PD or any event entering in the definition of PFS after 2 or more consecutive missing or inadequate tumor assessments	Right censored at last adequate assessment before the consecutive missing/inadequate assessments	Right censored at last adequate assessment before the consecutive missing/inadequate assessments	Not applicable
Initiation of a new anticancer treatment for the disease under investigation before any event entering in the definition of PFS	Right censored at their last adequate assessment before the initiation of the new anticancer treatment	Not applicable	Not applicable
No death, PD, nor any event entering in the definition of PFS	Right censored at the date of their last adequate assessment	Right censored at the date of their last adequate assessment	Right censored at the date of their last adequate assessment

Abbreviations: PD: Progressive disease; PFS: Progression-free survival.

The secondary endpoint analysis of PFS will consist of the analyses as presented in Table 10 below and will follow the same methods as described for EFS. The PFS rates will be estimated be at 9, 12, 18, 24, 36, 48 and 60 months post-randomization.

Table 10: Analyses for PFS

Analysis	Population	Censoring rules (Table 7)	Endpoint	Statistical methods
Main	ITT	Primary	PFS as assessed by the BIRC	same as primary EFS analysis (Section 14.1.1), incl. Kaplan- Meier curves
Sensitivity	ITT	Primary	PFS as assessed by the investigator	same as primary EFS analysis (Section 14.1.1), incl. Kaplan- Meier curves

^{*}Any PFS event is considered as a post-baseline assessment.

Analysis	Population	Censoring rules (Table 7)	Endpoint	Statistical methods
Supplementary	ITT	Sensitivity #1	PFS as assessed by the BIRC	same as primary EFS analysis (Section 14.1.1), incl. Kaplan- Meier curves
Supplementary	ITT	Sensitivity #2	PFS as assessed by the BIRC	same as primary EFS analysis (Section 14.1.1), incl. Kaplan- Meier curves
Subgroups	ITT	Primary	PFS as assessed by the BIRC	same as EFS subgroup analysis (Section 14.1.4) only for subgroups defined in Section 8.2.1, and to be presented in a forest plot

The number and percentage of deaths due to any cause and disease progression (radiological or clinical) as assessed by the BIRC or the investigator respectively and censoring reasons will be presented by treatment arm for all 3 censoring scenarios as presented in Table 9.

The PFS time or censoring time and the reasons for censoring will also be listed for all 3 censoring scenarios as presented in Table 9.

14.2.3 Locoregional Control

Locoregional Control (LRC) time is defined as the time (in months) from randomization to the first occurrence of progression at the site of the primary tumor or the locoregional lymph nodes, either according to RECIST v1.1 or based on clinical assessment (radiological or clinical, as assessed by the investigator or the BIRC, respectively).

LRC = (date of PD (primary tumor or locoregional) – randomization date +1) / 30.4375

Censoring rules for the primary and sensitivity analyses of LRC are described in Table 11 below. The last adequate tumor assessment is defined as the last tumor assessment result that is not "Not evaluable" or "Not assessed". If a participant is meeting a multiple censoring situation, the earliest censoring criterion will be applied.

Table 11: Censoring rules for LRC

Situation	Primary	Sensitivity #1	Sensitivity #2
No evaluable baseline or post-baseline assessment	C	Right censored at the date of randomization	Right censored at the date of randomization
PD after 2 or more consecutive missing or inadequate tumor assessments	Right censored at last adequate assessment before the consecutive missing/inadequate assessments	Right censored at last adequate assessment before the consecutive missing/inadequate assessments	Not applicable
Initiation of a new anticancer treatment for the disease under investigation before any documented progressive disease	Right censored at their last adequate assessment before the initiation of the new anticancer treatment	Not applicable	Not applicable
No locoregional failure	Right censored at the date of their last adequate assessment	Right censored at the date of their last adequate assessment	Right censored at the date of their last adequate assessment

Abbreviations: LRC: Locoregional control; PD: Progressive disease

The secondary endpoint analysis of LRC will consist of the analyses as presented in Table 12 below and will follow the same methods as described for EFS. The LRC rates will be estimated be at 9, 12, 18, 24, 36, 48 and 60 months post-randomization.

Table 12: Analyses for LRC

Analysis	Population	Censoring rules(Table 9)	Endpoint	Statistical methods
Main	ITT	Primary	LRC as assessed by the investigator	same as primary EFS analysis (Section 14.1.1), incl. Kaplan-Meier curves
Sensitivity	ITT	Primary	LRC as assessed by the BIRC	same as primary EFS analysis (Section 14.1.1), incl. Kaplan-Meier curves

Analysis	Population	Censoring rules(Table 9)	Endpoint	Statistical methods
Supplementary	ITT	Sensitivity #1	LRC as assessed by the investigator	same as primary EFS analysis (Section 14.1.1), incl. Kaplan-Meier curves
Supplementary	ITT	Sensitivity #2	LRC as assessed by the investigator	Same as primary EFS analysis (Section 14.1.1), incl. Kaplan-Meier curves
Subgroups	ITT	Primary	LRC as assessed by the investigator	same as EFS subgroup analysis (Section 14.1.4) only for subgroups defined in Section 8.2.1, and to be presented in a forest plot

The number and percentage of disease progression (primary tumor or locoregional) as assessed by the BIRC or the investigator, respectively and censoring reasons will be presented by treatment arm for all 3 censoring scenarios as presented in Table 11.

The LRC time or censoring time and the reasons for censoring will also be listed for all 3 censoring scenarios as presented in Table 11.

14.2.4 Objective Response

Objective Response (OR) is defined as a best overall response (see Section 9.15 for the derivation) of CR or PR according to RECIST v1.1, as assessed by the BIRC or the investigator, respectively.

Each participant will have an objective response status (0: 'no OR'; 1: 'OR') at 9 and 12-months post-randomization.

Participants will be counted as non-responders in the assessment of OR, who

- do not have any evaluable post-baseline assessment,
- receive a new anticancer treatment prior to reaching CR or PR,
- only have non-measurable disease with a best overall response at non-CR/non-PD,
- progress, die, or drop out for any reason prior to reaching CR or PR.

The OR rate (ORR) is the proportion of participants with OR in the analysis set.

OR status as assessed by BIRC will be compared between the two treatment arms by using a logistic regression model adjusted for randomization stratification factors. The same stratification factors used for the randomization will be applied to the analysis. The number of participants with

OR will be summarized by treatment arm and presented along with the odds ratio and the corresponding 95% CI.

The SAS code for the logistic regression model is specified in Appendix 6

A sensitivity analysis will be performed based on the OR as assessed by the investigator.

The number and percentage of participants with a best overall response of CR, PR, SD, non-CR/non-PD, PD, and NE as assessed by the BIRC or the investigator, respectively will be summarized by treatment arm.

The best overall response of CR, PR, SD, non-CR/non-PD, PD, and NE as assessed by the BIRC or the investigator, respectively, will also be listed together with the OR status.

